### 5.2.5 Prior and Concomitant Therapy

All investigator terms for medications recorded in the CRF will be coded to an 11-digit code using the current version of the World Health Organization Drug Dictionary (WHO DD).

Prior medications will be defined as medications that started before the first dose of study drug. Concomitant medications will be defined as medications taken during the treatment period (defined as the period from first dose date to 28 days after last dose date).

Note that a medication can be categorized into multiple categories: it can be prior only, concomitant only, or combination of prior and concomitant.

The number (percentage) of subjects who took prior and concomitant medications will be summarized on the FAS by treatment groups, and by Anatomical Therapeutic Chemical (ATC) class (level 1 and level 3), as well as WHO DD preferred term (PT). All medications will be presented in subject data listings.

In addition, non-pharmacological procedures and palliative radiotherapy will be listed.

#### 5.2.6 Treatment Compliance

No analysis is planned.

### 5.3 Data Analysis General Considerations

#### 5.3.1 Pooling of Centers

Subjects from all centers will be pooled for all analyses.

#### 5.3.2 Adjustments for Covariates

Not applicable.

#### 5.3.3 Multiple Comparisons/Multiplicity

Not applicable.

#### 5.3.4 Examination of Subgroups

Per study design, efficacy endpoints will be evaluated by *ESR1* mutation status (mutant, wild type) defined in Analysis Subsets (Section 5.2.1) for subjects who started on 450 mg. Exploratory subgroup analysis will be performed by:

CCI

A large rectangular area of the page is completely blacked out, indicating that the content has been redacted. The word 'CCI' is printed in red at the top left corner of this redacted area.

#### 5.3.5 Handling of Missing Data, Dropouts, and Outliers

Subjects drop out and unevaluable for DLT evaluation would be replaced per protocol.

No imputation for missing data will be performed in general, unless it is indicated for specific considerations. The imputation rules for partial date in order to derive a variable for disease characteristics will be specified in the study analysis dataset specification. For incomplete dates involving efficacy and safety data such as adverse events, concomitant

medications, laboratory values, vital signs and ECGs, a conservative imputation will be used for calculation. The imputation rules will be specified in study analysis dataset specification with more details. For endpoints that determine the percentage of responders, subjects with unknown response will be treated as non-responders.

### 5.3.6 Other Considerations

Not applicable.

## 5.4 Efficacy Analyses

Tumors are evaluated every two cycles (8 weeks) by investigator's assessment based on RECIST 1.1. Assessments will continue until disease progression or initiation of new anti-cancer therapy. Detailed BOR derivation rule is included in [Appendix 13.1](#). Detailed PFS censoring is included in [Appendix 13.2](#).

[figure not shown]
All efficacy parameters will be summarized for the either RES or FAS, or both.

### 5.4.1 Primary Efficacy Analyses

Primary efficacy analysis will be performed for the primary endpoint ORR:

#### For ORR:

For testing purposes: two protocol specified hypotheses will be tested separately for subjects dosed prior to Amendment 6 and under/after Amendment 6:

For estimating purposes, ORR will be provided for RES and FAS (regardless of when subjects are dosed), presented by treatment groups, by *ESR1* mutation groups, or by PgR status. The detailed list of ORR analysis is included in Table 1:

**Table 1 List of ORR analyses**

Purpose	Analysis set	Presentation (grouping)
Protocol defined Hypothesis testing	RES subjects of RES	Single group
Protocol defined supportive for testing	RES dosed prior to Amendment 6	Treatment groups
Protocol defined Hypothesis testing	RES dosed under/after Amendment 6	Single group
Protocol defined	FAS	Treatment groups
Protocol defined	RES	Treatment groups
Protocol defined subgroup	FAS	ESR1 status (Mutant, Wild type)
Protocol defined		

*ESR1* = estrogen receptor 1 gene, FAS = Full Analysis Set, PgR = progesterone receptor, RES = Response Evaluable Set.

A listing of efficacy data will be provided for FAS, at least including RES flag, starting dose level and date, *ESR1* mutation status and PgR status.

#### 5.4.2 Additional Efficacy Analyses

Additional efficacy analyses will be performed for DCR, CBR, PFS, DOR and OS.

For DCR: estimated DCR and the corresponding Clopper-Pearson 2-sided 95% CI will be presented. The presentation strategy will be similar to the ORR analysis.

For CBR: estimated CBR and the corresponding Clopper-Pearson 2-sided 95% CI will be presented. The presentation strategy will be similar to the ORR analysis.

For PFS: The main analysis of PFS will follow the FDA censoring rule guidance: progression date is assigned to the earliest date when any RECIST 1.1-defined disease progression is

observed without missing more than one adequate radiologic assessments. Details are included in [Appendix 13.2](#).

The distribution of PFS will be estimated using Kaplan-Meier methodology. Median PFS and the corresponding 2-sided 95% CIs will be summarized by treatment groups, *ESR1* mutation groups, or PgR status. The PFS rate at 3, 6, 9, and 12 months will be estimated using the Kaplan-Meier Method and the corresponding 2-sided 95% CIs will be summarized. In addition, Kaplan-Meier plots of PFS will be presented.

In addition to the main PFS analysis, supportive analysis may be performed (specified in [Appendix 13.2](#)): 1) considering new anticancer therapy as events, 2) allowing subjects to have events after COVID-19 related censoring, 3) considering clinical PD as events.

A complete list of PFS analysis is included in Table 2:

**Table 2 List of PFS analyses**

Purpose	Analysis set	Presentation grouping [Table, Figure]
Protocol defined	FAS	Treatment groups [TF]
Protocol defined subgroup	FAS CCI [REDACTED]	ESR1 status (Mutant, Wild type) [T]
CCI [REDACTED]	[REDACTED]	[REDACTED]
[REDACTED]	[REDACTED]	[REDACTED]
[REDACTED]	[REDACTED]	[REDACTED]
[REDACTED]	[REDACTED]	[REDACTED]
[REDACTED]	[REDACTED]	[REDACTED]
Sensitivity analysis is not included in the table and will be detailed in TLG shells.		
ESR1 = estrogen receptor, F = figure, FAS = Full Analysis Set, G = graph, PFS = progression-free survival, PgR = progesterone receptor, T = table.		

For DOR, the analysis will include subjects with confirmed responses. The same logics in censoring rules as those for primary analysis of PFS will be applied. If there are  $\geq 7$  subjects with confirmed responses, the median of DOR will be estimated using Kaplan-Meier methodology; median DOR and the corresponding 2-sided 95% CI will be presented by treatment groups on RES. If there are  $< 7$  subjects with confirmed responses, DOR will be listed.

For OS, the distribution of OS will be estimated using Kaplan-Meier methodology. Median survival time and the corresponding 95% CI, survival rates at 6, 12, 18, 24, 30 and 36 months, and corresponding 95% CIs will be estimated using Kaplan-Meier method. The analysis will be presented by treatment groups, *ESR1* mutation groups, and PgR status.

In addition, waterfall plot of best percentage change may be provided for RES subjects started on the 450 mg dose and color-coded by *ESR1* mutation groups.

#### 5.4.3 Subgroup Analyses

Efficacy analysis (ORR, CBR, PFS) will be performed using the subgroups defined in [Section 5.3.4](#).

Detailed analyses are provided in [Section 5.4.1](#) and [5.4.2](#). Additional exploratory subgroup analyses may be performed.

### 5.5 Pharmacokinetic, Pharmacodynamic, Pharmacogenomic, and Other Biomarker Analyses

Details of the analysis methods for population PK modeling will not be described in this SAP but will be described in a separate analysis plan.

#### 5.5.1 Pharmacokinetic Analyses

Plasma concentrations of H3B-6545 will be tabulated and summarized by dose level, day, and time.

H3B-6545 PK parameters will be derived from plasma concentrations by noncompartmental analysis using actual times. Minimally, the following PK parameters will be calculated:  $C_{max}$ ,  $t_{max}$ ,  $AUC_{(0-t)}$ ,  $R_{ac}$ , and if data permit, area under the concentration-time curve from zero time extrapolated to infinite time ( $AUC_{(0-inf)}$ ), elimination half-life of H3B-6545 ( $t_{1/2}$ ), oral clearance (CL/F), and apparent volume of distribution ( $V_z/F$ ).

The effect of a high-fat meal on AUC and  $C_{max}$  of H3B-6545 will be analyzed by their ratios.

All the PK analysis will be included in a separate PK report.

#### 5.5.2 Pharmacodynamic, Pharmacogenomic, and Other Biomarker Analyses

CC1

A large rectangular area of the page is completely blacked out, indicating redacted content. The text 'CC1' is printed in red at the top left corner of this redacted area.

### 5.6 Safety Analyses

All safety analysis will be based on the Safety Analysis Set by treatment groups, with the following exceptions: the DLT analysis will be based on the Dose Evaluable Set; the Phase 2 endometrium effects sub-study analysis will be based on the Endometrium Safety Evaluable Set. Subgroup analysis of selected safety data will be performed by *ESR1* mutation groups, or by PgR status.

Safety data will be summarized on an “as treated” basis using descriptive statistics (eg, n, mean, standard deviation, median, minimum, maximum for continuous variables; numbers and percentages (n [%]) for categorical variables). Safety variables include exposure parameters, treatment-emergent adverse events (TEAEs), clinical laboratory parameters, vital signs, 12-lead ECG results, Holter ECG results, and endometrium assessment data. Study Day 1 for all safety analyses is defined as the date of the first dose of study drug. Safety summary will include post-baseline data during the treatment period (starting from first dose to last dose + 28 days).

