## 3.2 Overall Study Design and Plan

This is a first-in-human, multi-center, open-label, dose-escalation followed by dose expansion Phase 1/2 study of H3B-6545 for women with ER-positive, HER2-negative, locally advanced or metastatic breast cancer. The study contains a Phase 1 dose escalation part, and a Phase 2 dose expansion portion as shown below:

- The Phase 1 dose escalation part will follow a standard 3+3 cohort design to determine the MTD/RP2D. Once a subject has completed Cycle 3 at her assigned dose level of drug, intra-subject dose escalation will be allowed.

- The Phase 2 dose expansion part will examine the efficacy of the RP2D. Two substudies are included to examine the food effect on PK and effect of H3B-6545 on the endometrium. In addition, approximately [REDACTED] subjects having a clonal *ESR1* Y537S mutation, in the absence of *ESR1* D538G mutation are enrolled to examine the efficacy.

Abbreviations: DL=dose level; ER $\alpha$ mut=estrogen receptor alpha mutant; ER $\alpha$ WT=estrogen receptor alpha wild-type; MTD=maximum tolerated dose; PK=pharmacokinetics; PO=orally (by mouth); QD=once daily; RP2D=recommended Phase 2 dose.

All subjects entering this study will receive H3B-6545 PO once daily. Efficacy, safety and PK/PD will be assessed according to the Schedule of Assessments (Protocol Appendix E). Subjects are permitted to continue treatment with H3B-6545 until disease progression, unacceptable toxicity, or decision to discontinue treatment by the subject or the study physician. After discontinuation from protocol treatment, subjects must be followed for adverse events (AEs) for 28 days after their last dose of study drug. If a subject discontinues therapy for a reason other than disease progression, they will continue to be evaluated for response until disease progression or until they start a new anti-cancer therapy. Following disease progression, all subjects will be followed for survival at least every 12 weeks, and survival follow-up will end 6 months after the last subject receives their first dose of study treatment (at the time of data cutoff for the primary analysis) (as of Amendment 9), and no survival follow-up will be done in the Extension Phase.

The primary analysis for efficacy will be based on data collected 6 months after the last subject receives their first dose of study treatment.

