### 5.6.2.2 AE Data

Adverse events (AEs) will be collected for each subject until 28 days after last study drug administration. The NCI CTCAE v4.03 will be used for AE reporting.

The AE verbatim descriptions (investigator terms from the CRF) will be classified into standardized medical terminology using the Medical Dictionary for Regulatory Activities (MedDRA). Adverse events (AEs) will be coded to the MedDRA (version 19.1 or higher) lower level term (LLT) closest to the verbatim term. The linked MedDRA PT and primary system organ class (SOC) will also be captured in the database.

A treatment-emergent adverse event (TEAE) is defined as:

- An AE that emerged during treatment (from first dose of study drug up to 28 days after last dose), having been absent at pretreatment (Baseline) or
- Reemerged during treatment, having been present at pretreatment (Baseline) but stopped before treatment, or
- Worsened in severity during treatment relative to the pretreatment state (Baseline), when the AE was continuous.

The AEs will be summarized using the Safety Analysis Set. Only those AEs that were treatment-emergent (TEAE) will be included in summary tables. The incidence of TEAEs will be reported as the number (percentage) of subjects with TEAEs by SOC and PT. A patient will be counted only once within a SOC and PT, even if the patient experienced more than 1 TEAE within a specific SOC and PT. The number (percentage) of patients with TEAEs will also be summarized by maximum NCI CTCAE v4.03 grade, and by causal relationship to study drug (Yes [related] and No [not related]).

Number (percent) of subjects will be summarized by treatment groups in the following analysis:

- Overview of TEAEs (including TEAEs, TEAEs by maximum grade, TEAEs by relationship, treatment-emergent SAEs, treatment-related TEAEs, TEAEs leading to study drug discontinuation, TEAEs with Grade  $\geq 3$ , TEAEs leading to study drug reduction, TEAEs leading to study drug interruption, TEAEs leading to death)
- TEAEs by SOC and PT
- TEAEs by SOC, PT and maximum grade
- TEAEs by PT
- TEAEs of Grade  $\geq 3$  by SOC and PT
- Treatment-related TEAEs by SOC and PT
- Treatment-related TEAEs by SOC, PT and maximum grade
- Treatment-related TEAEs of Grade  $\geq 3$  by SOC and PT

- Treatment-emergent SAEs by SOC and PT
- Treatment-emergent SAEs by SOC, PT and maximum grade
- Treatment related treatment-emergent SAEs by SOC and PT
- TEAEs leading to study drug discontinuation by SOC and PT

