### 5.6.3 Laboratory Values

Laboratory results will be summarized by treatment groups on the safety analysis set. The analysis will include assessment collected at baseline and/or during treatment (from first dose to 28 days after last dose date), using Système International (SI) units, as appropriate. Values that are non-missing and reported as ‘below the detectable limit’ of an assay will be replaced by half of the detectable limit in the summary tables.

For all quantitative parameters, the numeric value and the change from baseline to each post-baseline visit (including end of treatment visit and safety follow up visit) will be summarized by visit using descriptive statistics. Qualitative parameters summarized by frequencies (number and percentage of subjects) at each post-baseline visit (including end of treatment visit and safety follow up visit) will be reported.

Furthermore, the frequency of laboratory abnormalities by maximum post-baseline CTCAE grade will be summarized for selected laboratory parameters, including hemoglobin, White Blood Cell Count (WBC), Absolute neutrophil count (ANC), lymphocytes, platelet count, alkaline phosphatase (ALP), aspartate aminotransferase (AST), alanine aminotransferase (ALT), bilirubin, creatinine, estimated glomerular filtration rate (eGFR, calculated using the Modification of Diet in Renal Disease [MDRD] formula), thyroid-stimulating hormone (TSH) and electrolytes. Shift tables will also be produced for selected parameters based on the baseline CTCAE grade and the maximum CTCAE grade at post-baseline visits.

Listings of laboratory results will be provided. In addition, a listing of potential Hy’s law cases will be provided, including subjects who meets one of the following criteria at any post-baseline timepoint (not necessarily at the same timepoint): (aspartate aminotransferase or alanine transferase) $>3 \times$  upper limit of normal (ULN). Parameters (AST, ALT, Total Bilirubin, ALP as multiples of ULN) at all timepoints will be included. Subjects meeting Hy’s Law definition will be discussed in the CSR based on FDA “Guidance for Industry Drug Induced Liver Injury: Premarketing Clinical Evaluations, July 2009”.

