### 5.6.4 Vital Signs

By-timepoint analysis: descriptive statistics for vital signs parameters (ie, systolic and diastolic blood pressure [BP], pulse/heart rate [HR], respiratory rate [RR], temperature and weight) during the treatment period and changes from baseline will be summarized by visit, presented by treatment groups on the Safety Analysis Set.

Categorical analysis: the number (percentage) of subjects who meet the criterion ([Table 3](#) and [Table 4](#)) with at least 1 post-baseline result during the treatment period will be summarized (based on worst post-baseline results), and presented by treatment groups:

Blood pressure will also be summarized using a shift table from baseline to worst post-baseline by categories defined based on CTCAE grades.

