#### 5.6.5.2 Central and Local 12-lead ECG Data

In addition, central triplicate 12-lead ECG are collected at screening, and on Day 1 and Day 15 of Cycle 1 (for Phase 2 subjects), Day 1 of Cycle 2, 3, and 4 (predose and 3 hours postdose), as well as at the End of Treatment (EOT) visit.

Local 12-lead ECG data maybe collected at scheduled visits starting from Cycle 5 until the last cycle prior to the EOT visit, and at unscheduled visits as clinically required.

For each ECG parameter (QTcF, PR, etc), the average of triplicate at each timepoint (screening, predose and post dose on Day 1 of Cycle 1, 2, 3, 4, EOT, unscheduled, etc) will be used in ECG analysis below:

- By-timepoint analysis: ECG parameters numerical results and changes from baseline at each scheduled timepoint (including EOT and safety follow up visit) during the treatment period will be summarized by treatment groups.
- Categorical analysis: the number (percentage) of subjects who meet the following criterion with at least 1 post-baseline ECG result during the treatment period will be summarized (based on worst post-baseline results) and presented by treatment groups:

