## 13 APPENDICES

### 13.1 General Rules Deriving Best Overall Response

The BOR is determined once all the data for the subject is known. For this study, a confirmation of complete responses or partial responses is required  $\geq 4$  weeks after the initial assessment of response. In order for SD to be considered the BOR, it must occur  $\geq 7$  weeks following the first dose of study drug. For subjects who do not have a target lesion at baseline, a timepoint response of Non-CR/Non-PD will be treated as SD in BOR derivation, and will be included in DCR and CBR calculation.

To program the BOR per RECIST, the rules below will be followed:

1. The tumor response data collected via the CRFs will be used
2. Any further response assessments after the first PD identified will not be considered for the BOR determination, however they will be presented in the data listings
3. Any tumor assessments after the subject starts a new anti-cancer therapy will not be considered
4. If there are 2 or more consecutive missing adequate tumor assessments, all subsequent assessments will not be considered for the determination of BOR.

Note that the duration between 2 adequate tumor assessments, as well as the duration between the last adequate tumor assessment and death or PD, will be used to identify the cases where 2 or more consecutive tumor assessments are missing. Using the start day and the end day to denote the study days of the two endpoints of the duration, duration = end day – start day. If the duration is longer than  $16\text{ weeks} + 2 \times 7\text{ days}$  (tumor assessment window) – 1 day (ie, 125 days), then it is considered that 2 or more consecutive adequate tumor assessments are missing.

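### The safety window runs to 28 days after the last dose with no stop at a new anticancer therapy, so a value taken after a switch can become the worst on-treatment laboratory or vital sign result

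*SAP*

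**What the plan says.** The safety window is the same wherever the SAP states it.

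- **Section 3.2 (design):** "subjects must be followed for adverse events (AEs) for 28 days after their last dose of study drug".
- **Section 5.6 (all safety summaries):** "Safety summary will include post-baseline data during the treatment period (starting from first dose to last dose + 28 days".
- **Section 5.6.2.2 (first limb of the TEAE definition):** "An AE that emerged during treatment (from first dose of study drug up to 28 days after last dose".
- **Section 5.6.3 (laboratory):** "The analysis will include assessment collected at baseline and/or during treatment (from first dose to 28 days after last dose date".
- **Section 8:** on-treatment assessments run from first dose to 28 days after last dose. On-treatment EOT and safety follow-up values go into every threshold analysis. Shift tables draw on scheduled and unscheduled visits alike.

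Several tables reduce these data to one extreme per subject.

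- **Laboratory (5.6.3):** "the frequency of laboratory abnormalities by maximum post-baseline CTCAE grade will be summarized for selected laboratory parameters".
- **Vital signs (5.6.4):** subjects "with at least 1 post-baseline result during the treatment period will be summarized (based on worst post-baseline results".
- **ECG (5.6.5.2):** subjects "with at least 1 post-baseline ECG result during the treatment period will be summarized (based on worst post-baseline results".

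Efficacy is handled differently. Section 13.1, rule 3 says "Any tumor assessments after the subject starts a new anti-cancer therapy will not be considered", and Table 7 No. 4 in Section 13.2 censors PFS when a new anticancer treatment starts.

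**The concern.** The next line of treatment has its own toxicity. If it begins within 28 days of the last dose of H3B-6545, the SAP still treats later laboratory and vital sign values as on-treatment. Because the tables keep only the highest grade or worst value, one post-switch sample can decide a subject's row. These tables carry no relatedness column, and every subject receives H3B-6545, so no comparison group shows the background.

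Safety and tolerability is a secondary objective in both phases. The laboratory and vital sign abnormality tables are part of how the study will describe the drug, and a reader could not tell which entries came after a switch. The potential Hy's law listing in Section 5.6.3 has the same weakness: it takes AST or ALT above 3 x ULN at any post-baseline timepoint, and Hy's law is the only reportable AESI (5.6.2.3).

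**Working it through.** The main check is textual, because the SAP gives no figure to reproduce.

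**Step 1. Is there a stop at new therapy in any safety rule?**

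| Place in SAP | Period or rule | Stop at new anticancer therapy? |
|---|---|---|
| 3.2, AE follow-up | 28 days after last dose | No |
| 5.6, all safety summaries | first dose to last dose + 28 days | No |
| 5.6.2.2, TEAEs | same | No |
| 5.6.3, laboratory | same | No |
| 5.6.4, vital signs | treatment period, worst result | No |
| 5.6.5.2, ECG | treatment period, worst result | No |
| 8, on-treatment definition | same 28 days | No |
| 13.1 rule 3, BOR | later tumor assessments ignored | Yes |
| 13.2 Table 7 No. 4, PFS | censored | Yes |

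**Step 2. Which tables have some protection?** TEAEs are summarized by related and not related, with separate treatment-related tables. The laboratory, vital sign and ECG tables have no such split.

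**Step 3. Which data can fall after a switch?** Safety follow-up values and unscheduled values within the 28 days can, and so can EOT values if that visit comes after the switch. For ECG there is less room. Central tracings are scheduled only up to the EOT visit, and local ones from Cycle 5 to the last cycle before EOT, plus unscheduled ones. The by-timepoint ECG analysis names the safety follow-up visit, but the collection schedule in 5.6.5.2 lists no ECG there.

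**Step 4. How large could the effect be?** Let p be the true proportion with a given abnormality on H3B-6545 and s the proportion who start a new therapy within the window. Let q be the chance that such a subject then has that abnormality recorded before the window closes. If these are independent:

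tabulated proportion = p + (1 − p) × s × q

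The SAP gives none of p, s or q. All the values below are assumptions.

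| p | s | q | Added points | Tabulated |
|---|---|---|---|---|
| 2% | 10% | 10% | 0.98 × 0.10 × 0.10 = 1.0 | 3.0% |
| 2% | 30% | 20% | 0.98 × 0.30 × 0.20 = 5.9 | 7.9% |
| 2% | 50% | 40% | 0.98 × 0.50 × 0.40 = 19.6 | 21.6% |
| 20% | 30% | 5% | 0.80 × 0.30 × 0.05 = 1.2 | 21.2% |
| 20% | 70% | 20% | 0.80 × 0.70 × 0.20 = 11.2 | 31.2% |

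If nobody switches within 28 days, or nobody is sampled after switching, the addition is zero. The table shows how the effect depends on its inputs and does not estimate it for this trial.

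**The case against.** The strongest reply is that a window of last dose + 28 days is a common, deliberately inclusive convention, applied consistently throughout this SAP. That stands. A reader might infer from the efficacy rules that the SAP contradicts itself. It does not: cutting tumor data isolates drug efficacy, while an all-cause safety window aims not to miss late effects.

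A reader might also infer that the TEAE tables wrongly credit next-line toxicity to H3B-6545. The documents do not support this. Treatment-emergent is defined by timing, and causality is reported separately. Moving TEAEs out of the main rows would rest on unblinded investigator judgment in a first-in-human study and could understate late toxicity.

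A third tempting reading is that many subjects switch quickly and that the distortion differs by dose, *ESR1* or PgR group. The SAP gives no switching rates. The 15% trigger in Section 13.2 shows that the sponsor foresaw censoring for new therapy, but it is a threshold for a PFS sensitivity analysis and says nothing about timing within 28 days.

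Other points stand in part:

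- The visit schedule is in the protocol, which is not at hand, and further conventions are left to separate specifications. The SAP nevertheless fixes the window itself and mentions no exception.
- By-visit tables show EOT and safety follow-up separately, and all the data are listed. This helps a careful reader but does not correct the worst-value tables.
- The DLT analysis and ORR are unaffected, and the visible text ties no decision rule to the affected tables.

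**Conclusion.** The point holds as a weakness of attribution in the maximum-grade, shift and worst-value tables for laboratory values and vital signs. It holds for ECG only where post-EOT or unscheduled tracings exist. Followed as written, the SAP counts a value taken after a switch within 28 days as on-treatment, and nothing in those tables reveals it.

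The direction is clear: for abnormality counts, extra post-switch data can only leave the worst value unchanged or make it worse. The size is not known. It depends on how many subjects start a new therapy within 28 days and are sampled afterwards, which the documents do not give. This is a worthwhile, inexpensive improvement to descriptive tables. It is no ground for changing the TEAE definition or for claiming a demonstrated bias between groups.

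**What to change.** **Change, in Sections 5.6 and 8:**

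1. Produce the laboratory, vital sign and ECG maximum-grade, shift and worst post-baseline tables with data up to the earlier of last dose + 28 days and the day before a new anticancer therapy starts. This can be the main table or stand beside the full 28-day table. Showing both loses no information.
2. Flag records on or after the start of new therapy in the laboratory, vital sign and ECG listings, including the potential Hy's law listing.
3. Leave the TEAE definition and main TEAE tables unchanged. Flag TEAEs with onset on or after the new therapy in the AE listings.

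**Cost:** a sentence or two of SAP text, one date condition in programming and, if both versions are shown, some extra tables. BOR and PFS already need the start date of new therapy. Those derivations use it only for switches before progression, so confirm that it is also recorded for subjects who switch after progression. The concomitant medication period in Section 5.2.5 covers the same 28 days.

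**Downside:** a late laboratory effect of H3B-6545 appearing after a switch would be seen only in the full-window table or the listing. A sample taken on the day the new therapy starts, but before its first dose, would also fall outside the truncated table.
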